8 SAFETY ANALYSES

8.1 Adverse Events

Adverse Events (AEs) will be summarized by frequency and percentage. AEs will be coded using the Medical Dictionary for Regulatory Activities (MedDRA) (Version 20.0 or later). An AE occurring between the first administration of study medication to the end of the study is considered a Treatment-Emergent Adverse Event (TEAE). All TEAEs will be summarized by treatment group. Counts and percents will be presented by treatment group for each observed system organ class (SOC) and preferred term (PT) as defined in MedDRA. The SOCs and PTs will be summarized in the following set of tables for the Safety Population:

- All AEs
- All AEs by maximum level of severity
- All AEs by closest attribution to the study medication.

Adverse events that occur during the screening period will be listed.

8.2 Clinical Laboratory Evaluation

Clinical laboratory assessments taken from blood sampling such as hematology, chemistry, PT and INR will be summarized and listed for the Safety Population.

Pregnancy test results and clinical laboratory values from urine samples will be listed for the Safety Population.

8.3 Vital Signs

Vital signs (heart rate, respiratory rate, systolic blood pressure, diastolic blood pressure and weight, and BMI) will be presented in a table with summary statistics by visit for the Safety Population. Height will be summarized for the Screening visit.

8.4 Physical Exam

Physical examination assessments will be listed by subject, visit and exam type. All exams will be listed for the baseline observation; Only abnormal results will be presented in the listings for the post baseline visits.

8.5 Safety Labs

Safety labs, Prothrombin Time (PT) and International Normalized Ratio (INR) and their associated CFB values will be summarized and listed.

9. CHANGES IN THE STATISTICAL METHODS FROM THOSE STATED IN THE PROTOCOL

The secondary variables will be analyzed with the ITT population only.

10 APPENDIX

Appendix A

Normal Approximation to the Binomial Distribution Test

Let n_1 and n_p denote the sample sizes and let m_1 and m_p denote the number of responses for Ifetroban (200mg/day), and Placebo, respectively. Furthermore, let $r_1 = m_1/n_1$, and $r_p = m_p/n_p$, denote the sample proportions for Ifetroban (200mg/day) and Placebo, respectively. Note that 'r' is used to denote proportions instead of the standard 'p' because p is being used to denote the p-value.

let

$$Z_{1p} = (r_1 - r_p)/s_{1p}$$

where

$$s_{1p} = \{r_1(1-r_1)/n_1 + r_p(1-r_p)/n_p\}^{1/2}.$$

The corresponding p-value is $p=1-\Phi(Z_{1p})$ where Φ is the standard normal distribution function and is calculated using the *PROBNORM* SAS function in the data step.

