#### **Secondary Analyses**

CFB in ACQ-7 and CFB in TNSS at Week 8 will be analyzed using ANCOVA, with the corresponding value at Baseline included as the only covariate. These variables, as well as CFB in SNOT-22, at Week 4 will also be analyzed as ancillary analyses.

Analyses of CFB for other continuous efficacy variables at Weeks 4 and 8 will be performed as ancillary analyses using ANCOVA with the corresponding value at Baseline included as the only covariate. Responder analyses, defined as any improvement in SNOT-22, ACQ-7, and TNSS (Yes or No) at Weeks 4 and 8 will be performed as ancillary analyses using the normal approximation to the binomial distribution, assuming unequal variances.

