4.5 Sample Size Determination

Thirty-eight subjects per group will provide 90% power for the comparison of ifetroban and placebo with respect to the change from baseline in SNOT-22 scores at Week 8 (two-sided, level 0.05), assuming a common standard deviation of 16 and a true difference is 12.

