7 EFFICACY ANALYSES

All hypothesis tests will be performed at the 0.05 level. Analyses of the primary efficacy variables will be performed using both the ITT and PP Populations; analyses of secondary efficacy variables will be performed using the ITT population only. Summary statistics will be presented for all analyses of efficacy variables.

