7.1 Primary Efficacy Analysis

The primary analysis of interest is the CFB in SNOT-22 at week 8 on the ITT population, imputed with LOCF. Between-treatment comparison will be performed using Analysis of Covariance (ANCOVA) with SNOT- 22 at baseline and treatment in the model. The p-value associated with the difference between the treatments in least squares will determine significance. Least squares (LS) means, differences in LS means and the associated p-value, corresponding standard errors, and corresponding confidence intervals will be presented in a table. To assess sensitivity, this analysis will also be performed on the CFB SNOT-22 imputed using MI (Section 5.1).

The chart below outlines the analyses to be performed on each variable. It identifies the weeks for which the analysis will be performed for the corresponding variable, population, and type of imputation.

Variable Name	Value Type	Pop	Weeks for Analysis		Sensitivity (1)
			Summary	ANCOVA	
SNOT-22	Score Value	ITT/PP	0,4,8,10		LOCF
	Score CFB	ITT/PP	0,4,8,10	4,8,10	LOCF/MI

(1) Imputation analysis outlined in Section 5.1. LOCF=Last observation carried forward, MI=Multiple Imputation

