7.2 Secondary Efficacy Analyses

The analyses performed for the secondary efficacy variables will be combinations of summary statistics and ANCOVAs, using the normal approximation to the binomial (see Appendix A for details.) as appropriate, at specified visits presented in the table below.

The ANCOVA will include the corresponding value at Baseline as the only covariate with treatment. The LS means, standard error and p-values will be presented with corresponding the summary statistics.

Categorical variables will be analyzed using the normal approximation to the binomial distribution, assuming unequal variances. The p-value will be presented along with summary statistics.

The chart below outlines the analyses to be performed on each variable. It identifies the weeks in which the analysis will be performed for the variable of interest, the population, and the type of imputation.

Variable Name	Value Type	Pop	Weeks for Analysis			Imputation (2)
			Summary	ANCOVA	Binomial (1)	
SNOT-22	Score PCFB	ITT	0,4,8,10			LOCF
	Improvement(y/n)	ITT	0,4,8,10		4,8,10	NRI
SNOT-22 Subscale	Nasal Related	ITT	0,4,8,10			LOCF
	Ear and Facial	ITT	0,4,8,10			LOCF
	Quality of Life	ITT	0,4,8,10			LOCF
	Psychological	ITT	0,4,8,10			LOCF
	CFB Nasal Related	ITT	0,4,8,10			LOCF
	CFB Ear and Facial	ITT	0,4,8,10	4,8,10		LOCF
	CFB Quality of Life	ITT	0,4,8,10	4,8,10		LOCF
	CFB Psychological	ITT	0,4,8,10	4,8,10		LOCF
	22 Questions	ITT	0,4,8,10			LOCF
FEV1	Value	ITT	0,4,8,10			LOCF
	CFB	ITT	0,4,8,10	4,8,10		LOCF
PNIFR	Value	ITT	0,4,8,10			LOCF
	CFB	ITT	0,4,8,10	4,8,10		LOCF
UPSIT	Value	ITT	0,4,8,10			LOCF
	CFB	ITT	0,4,8,10	4,8,10		LOCF
FeNO	Value	ITT	0,4,8,10			LOCF
	CFB	ITT	0,4,8,10	4,8,10		LOCF
ACQ	Value	ITT	0,4,8,10			LOCF
	CFB	ITT	0,4,8,10	4,8,10		LOCF
	Improvement (y/n)	ITT	0,4,8,10		4,8,10	NRI

(1) Normal approximation to the Binomial
 (2) Imputation analysis outlined in Section 5.1. NRI=Non responder imputation, LOCF=Last observation carried forward

Variable Name	Value Type	Pop	Analysis			
			Summary	ANCOVA	Binomial (1)	Imputation (2)
TNSS AM/PM	Visit Score	ITT	4,8,10			LOCF
	CFB Visit score	ITT	4,8,10	4,8,10		LOCF
Asthma	Reports	ITT	0,4,8,10			LOCF
	CFB Reports	ITT	0,4,8,10	4,8,10		LOCF
	Max Severity	ITT	0,4,8,10			LOCF
	Rescue report	ITT	0,4,8,10			LOCF
	CFB rescue report	ITT	0,4,8,10	4,8,10		LOCF
Sinusitis	Reports	ITT	0,4,8,10			LOCF
	CFB Reports	ITT	0,4,8,10	4,8,10		LOCF
	Max Severity	ITT	0,4,8,10			LOCF
	Antibiotic report	ITT	0,4,8,10	4,8,10		LOCF

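### SAP Appendix A computes the responder p-value as a one-sided upper tail in ifetroban's favour without saying so, and the result is read against 0.05

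*SAP*

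**What the plan says.** SAP section 7.2 sets the method for the responder variables: "Categorical variables will be analyzed using the normal approximation to the binomial distribution, assuming unequal variances". It refers to Appendix A for the details and gives no sidedness. Its table assigns this test to SNOT-22 improvement and ACQ improvement at Weeks 4, 8 and 10, which makes six tests. A responder is a subject whose change from baseline is below zero (SAP section 4.6), so a higher rate is the better result.

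Appendix A takes the ifetroban rate minus the placebo rate, divides by an unpooled standard error to get Z, and then states: "The corresponding p-value is $p=1-\Phi(Z_{1p", i.e. p = 1 − Φ(Z), computed with the SAS normal distribution function. It neither doubles the tail nor takes an absolute value.

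On the level, SAP section 7 says: "All hypothesis tests will be performed at the 0.05 level". Protocol section 11.6.3 says the same, and neither gives sidedness. The sample-size text (Protocol Synopsis, Protocol 11.1, SAP 4.5) specifies "two-sided, level 0.05" for the SNOT-22 change at Week 8. The Protocol Synopsis says that the Week 4 and 8 responder analyses "will be performed as ancillary analyses using the normal approximation to the binomial distribution, assuming unequal variances", again without sidedness. SAP section 9 lists one change from the protocol: "The secondary variables will be analyzed with the ITT population only". SAP section 5.4 makes no multiplicity adjustment.

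**The concern.** Appendix A is a programming instruction. Followed as written, it produces a one-sided p-value that is compared with 0.05 in a trial whose only stated sidedness is two-sided. No sentence in either document calls the responder test one-sided or gives a reason for it.

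Two consequences follow. A responder difference in ifetroban's favour can be reported as significant when a two-sided test at the same level would not be. In the other direction, the p-value can never reach 0.05 when the ifetroban rate is the lower one, however large the gap. Responder rates from a proof-of-concept trial are easy to quote, and with no multiplicity adjustment each of the six p-values is read against 0.05 as it stands.

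**Working it through.** **1. What level was the trial planned at?** Inputs from SAP 4.5: 38 per group, difference 12, SD 16, power 90%.

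- Standardised effect: 12 / (16 × √(2/38)) = 3.269.
- Two-sided 0.05: power = Φ(3.269 − 1.960) = 0.905 (0.897 with the noncentral t, 74 df). This reproduces the stated 90%.
- One-sided 0.05: power = Φ(3.269 − 1.645) = 0.948, which does not.

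So the primary comparison was sized at two-sided 0.05.

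**2. What does the Appendix A rule do?** 1 − Φ(Z) < 0.05 means Z > 1.645. A two-sided p = 2(1 − Φ(|Z|)) < 0.05 gives a claim for ifetroban only if Z > 1.960. The nominal chance of a false claim for ifetroban is therefore 0.05 against 0.025 per test.

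**3. Exact size at 38 per arm.** I enumerated all pairs of two independent Binomial(38, p) counts, with the Appendix A unpooled standard error and equal true rates. The documents give no responder rates, so the range of p is an assumption.

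| True rate, both arms | Appendix A, claim for ifetroban | Two-sided, claim for ifetroban | Two-sided, both directions |
|---|---|---|---|
| 0.3 or 0.7 | 5.63% | 2.94% | 5.87% |
| 0.4 or 0.6 | 5.88% | 2.60% | 5.21% |
| 0.5 | 5.12% | 2.54% | 5.08% |
| 0.8 | 5.86% | 2.86% | 5.72% |
| 0.9 | 5.93% | 2.92% | 5.84% |

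The ratio of the second column to the third is 1.9 to 2.3. All Appendix A rejections favour ifetroban, so its total error (5.1% to 5.9%) is about the same as the two-sided total in the last column.

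**4. Worked cases.**

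- Ifetroban 28/38 = 0.737, placebo 21/38 = 0.553: difference 0.184, SE = √(0.737 × 0.263/38 + 0.553 × 0.447/38) = 0.108, Z = 1.71. Appendix A p = 0.044; two-sided p = 0.087. A two-sided test needs 29 ifetroban responders (p = 0.047).
- Ifetroban 21/38, placebo 30/38: Z = −2.27. Appendix A p = 0.99; two-sided p = 0.023. Any negative Z gives an Appendix A p above 0.5.

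**5. How far the threshold moves.** For each placebo count from 11 to 31 of 38, Appendix A reaches significance with 1 or 2 fewer ifetroban responders than the two-sided test. For 32 to 34 the gap is 0 or 1.

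**6. When ifetroban truly helps.** With assumed placebo rates of 0.4 to 0.7 and a true gain of 10 to 20 points, Appendix A is significant and the two-sided test is not in 9.2% to 15.2% of trials per test. Because the benefit is real in these cases, this measures the power the two-sided test gives up. It does not count false claims. At 0.75 against 0.55, power is 61% under Appendix A and 47% two-sided.

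**The case against.** The strongest reply is that the rule is fully pre-specified. Appendix A gives the direction, the standard error and the tail, and section 7.2 refers to it, so the test is unlabelled but not hidden. A one-sided test at 0.05 is still a test at the 0.05 level. The two-sided wording belongs to the sample-size statement for the primary endpoint, and the protocol set no sidedness for the responder tests, so SAP section 9 had no explicit rule to record a departure from. This much stands: that two-sided testing was intended throughout is an inference, though the only one the documents support.

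It is also fair that the consequence is bounded. Total type I error is not inflated. The primary result rests on the ANCOVA: "The primary analysis of interest is the CFB in SNOT-22 at week 8 on the ITT population, imputed with LOCF". The protocol calls the Week 4 and 8 responder analyses ancillary, and the ANCOVAs on the same instruments, with the summary statistics, would still show a difference in placebo's favour. The table shells are not in the supplied documents, so a footnote giving the sidedness may exist there. These points limit the severity. They leave the formula and the missing declaration as they are.

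**Conclusion.** The concern holds. As written, Appendix A yields an undeclared one-sided test in ifetroban's favour, read at 0.05, for six secondary responder comparisons. Per test, a false claim for ifetroban is about twice as likely as under a two-sided 0.05 test: 5.1% to 5.9% against 2.5% to 2.9%, with 38 analysed per arm and assumed common response rates of 0.3 to 0.9. Overall alpha is not raised; it is all placed on one side. The primary analysis is untouched. This should be fixed, but it does not threaten the trial's main conclusion.

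**What to change.** In Appendix A, replace the formula with p = 2*(1-PROBNORM(ABS(Z))). In SAP section 7, state that all hypothesis tests, including the responder tests, are two-sided at 0.05. Declaring the test one-sided at 0.025 would give the same threshold for a claim in ifetroban's favour, but the p-value would still be uninformative when placebo does better, so the two-sided form is preferable.

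The cost is one line of SAS code and one sentence of text. SAP section 1 already provides for review and revision before any unblinded analysis, which is when the change must be made. The downside is that favourable responder p-values double and power for these tests falls, for example from 61% to 47% at assumed rates of 0.75 against 0.55.
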